### **5.5. Justification for Dose**

The approved dosage and administration of dulaglutide in Japan is 0.75 mg once weekly, given subcutaneously. The dosage and administration were established based on Phase 2 and 3 studies in Japanese patients with T2D (Terauchi et al. 2014; Araki et al. 2015; Emoto et al. 2015; Miyagawa et al. 2015; Odawara et al. 2016).

## 6. Study Population

The planned patient population includes Japanese adult patients with T2D who have inadequate glycemic control with insulin therapy with or without OADs.

Prospective approval of protocol deviations to recruitment and enrollment criteria, also known as protocol waivers or exemptions, are not permitted.

### 6.1. Inclusion Criteria

Patients are eligible to be included in the study only if they meet all of the following criteria at Visit 1 except criterion [4]:

- [1] have T2D (based on the World Health Organization's [WHO] diagnostic criteria [[Appendix 5](#)]);
- [2] have been treated with insulin therapy (basal insulin [once or twice daily], premixed insulin [twice or 3 times daily], or basal/mealtime insulin [4 or 5 times daily] regimen) with or without 1 or 2 OADs at stable dose for at least 3 months prior to Visit 1;
- [3] doses of daily insulin must be stable ( $\pm 20\%$  versus the most commonly used dose for the period) and more than 10 units per day during the 3-month period prior to Visit 1;
- [4] have an HbA1c value  $\geq 7.0\%$  and  $\leq 10.5\%$  at Visit 1 if the patient is washing out OADs (DPP-4 inhibitors, SU, or glinides) or  $\geq 7.5\%$  and  $\leq 10.5\%$  at Visit 1 if the patient is not washing out OADs. At Visit 2, have an HbA1c  $\geq 7.5\%$  and  $\leq 10.5\%$  (values at Visit 1 and Visit 2 as assessed by the central laboratory);
- [5] have stable weight ( $\pm 5\%$ )  $\geq 3$  months prior to Visit 1;
- [6] have body mass index (BMI) of 18.5 to 35 kg/m^2 at Visit 1;
- [7] Japanese men or nonpregnant, nonbreastfeeding Japanese women aged  $\geq 20$  years at Visit 1;
- [8] are females of childbearing potential who must:
  - [a] test negative for pregnancy at Visit 1;
  - [b] agree to remain abstinent, use 1 highly effective method of contraception (ie, combined oral contraceptive pill and mini-pill, Nuva-Ring, implantable contraceptives, injectable contraceptives, intrauterine device, contraceptive patch [ONLY women <90 kg], or partner with vasectomy) or use a combination of 2 effective methods (ie, condom with spermicide, diaphragm with spermicide, female condom with spermicide, cervical sponge, cervical cap with spermicide) for the entire study. Abstinence or contraception must continue following completion of investigational product administration for 4 weeks following the last dose of investigational product.

[c] not be breastfeeding.

Women not of childbearing potential may participate and are defined as:

- a) infertile due to surgical sterilization (hysterectomy, bilateral oophorectomy, or tubal ligation), congenital anomaly such as mullerian agenesis; or
- b) postmenopausal woman  $\geq 50$  years of age with an intact uterus, who has not taken hormones or oral contraceptives within 1 year, AND
  - i) who has had either cessation of menses for at least 1 year, OR
  - ii) 6 months of spontaneous amenorrhea with follicle-stimulating hormone  $>40$  mIU/mL.

[9] have given written informed consent to participate in the study in accordance with local regulations and the ethical review board (ERB) governing the study site.

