**Study Schedule, Protocol H9X-JE-GBGF**

- f For each parameter, 3 measurements will be taken 30 seconds apart using the same arm. An appropriately sized cuff (cuff bladder encircling at least 80% of the arm) should be used to ensure the accuracy of blood pressure (BP) measurements. The arm used for the BP measurement should be supported at heart level.
- g A single 12-lead ECG will be performed locally and recorded, after the patient has been lying supine for 5 minutes. If the subject has a single 12-lead ECG record which was performed within 3 months prior to Visit 1, the data can be used as a baseline measurement.
- h Serum pregnancy test to be performed by the central lab at Visits 1 and 3 for women of childbearing potential only. Subsequent pregnancy tests can be performed as required at local laboratories. A local (urine) pregnancy test may additionally be performed at the investigator's discretion during the study.
- i Fasting laboratory samples must be obtained after a fast of 8 hours or more without eating, drinking (except for water), or performing any significant physical activity.
- j Patients are required to measure their fasting (pre-breakfast) plasma glucose (FPG) concentration at least once every 2 to 3 days at approximately the same time of day after Visit 3. By the investigator's decision, the frequency of measurement of FPG could be increased.
- k 7-point SMPG profiles (blood glucose measurements before breakfast, lunch, dinner, and bedtime and 2 hours after breakfast, lunch, and dinner) should be performed on 2 days within the 2 weeks prior to Visit 3 (Week 0), Visit 7 (Week 16), and ET visit (only when the patient discontinued before Week 16).

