#### Pregnancy test (serum)g

#### HbA1c

#### Glucose, fasting

#### Calcitonin

#### Pancreas (exocrine)

Total amylase  
 Lipase  
 Trypsin

- g A serum pregnancy test will be performed at Visit 1 and Visit 3 for women of childbearing potential only and will be analyzed at a central laboratory. Pregnancy tests may be repeated at any time during the study and analyzed locally at the investigator's discretion.

---

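### The repeat pregnancy test is drawn at the visit of randomization and first dispensing and sent to the central laboratory, and nothing requires a negative result before the first blinded dose

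*Protocol*

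**What the plan says.** Protocol Section 6.1 opens by saying that patients are eligible "only if they meet all of the following criteria at Visit 1 except criterion [4" (criterion [4] is the HbA1c range). Two criteria concern pregnancy, and both fall under that opening line. Criterion [7] admits "Japanese men or nonpregnant, nonbreastfeeding Japanese women aged" 20 years or older, and [8][a] requires women of childbearing potential to "test negative for pregnancy at Visit 1". Criterion [8][b] adds that they must "agree to remain abstinent, use 1 highly effective method of contraception" or a combination of two effective methods, for the whole study.

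On testing, footnote h of the Schedule of Activities (Section 2) reads "Serum pregnancy test to be performed by the central lab at Visits 1 and 3 for women of childbearing potential only". It then makes further testing optional: "A local (urine) pregnancy test may additionally be performed" at the investigator's discretion. Appendix 2, note g, agrees: "Pregnancy tests may be repeated at any time during the study and analyzed locally", again at the investigator's discretion.

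The Schedule and Section 7.2 place randomization at Visit 3, and the Schedule marks the first dispensing of investigational product at the same visit. Section 8.1.1 requires immediate discontinuation of a patient who becomes pregnant during the study. Section 9.2.1 has pregnancies reported through the SAE process so that outcomes are followed.

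**The concern.** The sponsor evidently wanted a second pregnancy check at the start of treatment, since one is scheduled there. As written, that check does no work before the first dose. The sample leaves the site on the day the patient is randomized and handed study drug, and the protocol does not say that anyone must see the result first. The last negative result the protocol insists on can be weeks or months old by then.

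At stake is a brief, avoidable exposure of a detectable early pregnancy to blinded study drug. This is a participant-safety point and does not touch the efficacy analysis.

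**Working it through.** The plan states no figure for doses taken before the Visit 3 result, so there is nothing to reproduce. The check has three steps.

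**1. Does any provision require a negative result before dosing?**

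- Section 6.1: [7] and [8][a] are judged at Visit 1. Only criterion [4] is extended, with "values at Visit 1 and Visit 2 as assessed by the central laboratory".
- Section 5.1: eligibility is reconfirmed at Visit 2, but the Schedule has no pregnancy test there.
- Schedule footnote h and Appendix 2 note g: the Visit 3 test is central; a local test is optional.
- Section 7.2: randomization at Visit 3 depends on meeting the enrollment criteria, which leads back to Visit 1 for pregnancy.
- Section 7.2.1.3: removal before randomization covers patients on oral antidiabetic drugs who develop a contraindication. It creates no pregnancy check.
- Section 8.1.3: covers patients who did not meet enrollment criteria. A woman who conceives after Visit 1 did meet [7] and [8][a] when they were judged.
- Section 8.1.1: acts once a pregnancy is known.

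None makes randomization, dispensing or first injection wait for the Visit 3 result.

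**2. How old is the last required negative test at first dosing?**

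Schedule footnote d gives the gap from Visit 1 to Visit 3; the Visit 1 window is ±7 days.

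- No washout: 4 × 7 = 28 days (21 to 35 with the window).
- Washout: 14 × 7 = 98 days (91 to 105 with the window).

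**3. How many doses can precede the Visit 3 result?**

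Inputs: once-weekly dosing (Section 7.2.1.1); cartons of 4 weekly pens (Section 7.1.1); Visit 4 at Week 4 (Schedule). Assumptions, because the documents do not say: the first injection is on the Visit 3 day (day 0), one carton is dispensed at Visit 3, and the result arrives on day t. Doses then fall on days 0, 7, 14 and 21, and the count is the number of those days before t.

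| Result known on | Doses already taken |
|---|---|
| Before first injection (site waits or tests locally) | 0 |
| Days 1-7 | 1 |
| Days 8-14 | 2 |
| Days 15-21 | 3 |
| Days 22-28 | 4 (one carton used) |

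If an injection due on the day of the result is taken first, day 7 gives 2 and day 14 gives 3.

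The schedule gives only indirect evidence on t. Visit 1 results are expected by the Week -12 contact after a Week -14 draw (14 days). The Visit 2 HbA1c is needed for stratification at Visit 3, nominally 14 days later, or 7 days if Visit 2 falls at the late end of its window (14 - 7). Central results are thus expected within one to two weeks, which makes the rows with 1 or 2 doses the likeliest, but this is visit spacing and not a stated turnaround for the pregnancy assay.

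Share on active drug under 3:1 allocation: 120 / 160 = 0.75.

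**The case against.** The strongest reply is that several controls already surround this event. There is a negative test at Visit 1, contraception or abstinence for the whole study, a mandatory second serum test, permission to test locally at any time, immediate discontinuation, and outcome follow-up. A careful site would test locally or wait. The documents give no number of women of childbearing potential and no estimate of fetal risk from one or two weekly doses. All of this stands. It makes the event rare and brief, and it is why no case count or harm estimate is offered. It does not remove the gap: contraception can fail, the local test is discretionary, and discontinuation follows knowledge of the pregnancy.

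A reader might infer three stronger things that the documents do not support.

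- *That a woman known to be pregnant could be randomized and kept on treatment because she satisfied 6.1 at Visit 1.* Section 8.1.1 requires her to discontinue. Appendix 1 counts a patient as entered once consent is signed, so its wording can be read to cover the lead-in. The gap concerns an unrecognised pregnancy only.
- *That exposure cannot exceed two doses.* That limit would rest on visit spacing and an assumed injection day. The firmer ceiling is the 4-pen carton.
- *That every such woman would receive dulaglutide.* About one in four would receive placebo.

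**Conclusion.** The point holds as a cheap safety improvement that should be made. A site that follows the schedule exactly can give blinded study drug to a woman whose pregnancy was detectable that day.

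The likely size is 1 dose, or 2 with a result in the second week. This assumes a first injection on the Visit 3 day and a turnaround in line with the schedule's spacing. Without the turnaround assumption, one carton caps it at 4 doses by Visit 4. It is 0 wherever the site waits or tests locally. The number of women affected cannot be estimated from the documents and is expected to be small. The primary endpoint, alpha, power and sample size are unaffected.

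**What to change.** For women of childbearing potential, require a negative local urine pregnancy test at Visit 3, read before randomization and first dose. Keep the central serum sample as confirmation.

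Four places need editing:

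- **Section 6.1, [8][a]:** add the Visit 3 urine test to the Visit 1 requirement.
- **Section 6.1, opening line:** exempt [8][a] as well as [4] from being judged at Visit 1; otherwise the new condition contradicts it.
- **Schedule footnote h:** make the local urine test mandatory at Visit 3 and state that it comes before randomization; leave it discretionary at other times.
- **Appendix 2, note g:** the same change.

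The cost is one local urine test, of a kind the protocol already permits, per woman of childbearing potential. No visit is added. For a pregnancy detectable at Visit 3, the exposure falls to 0 doses. A conception too recent for the test to detect would still be missed, so contraception, the serum test and the discontinuation rule remain necessary.

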## 6.2. Exclusion Criteria

Patients will be excluded from study enrollment if they meet any of the following criteria at Visit 1:

- [10] have type 1 diabetes (based on WHO diagnostic criteria);
- [11] have previously received therapy with a GLP-1 receptor agonist within 3 months prior to Visit 1;
- [12] have been previously treated with dulaglutide prior to Visit 1;
- [13] have been treated with 2 of the following at Visit 1: DPP-4 inhibitor, SU, and glinide (ie, DPP-4 inhibitor and SU, or DPP-4 inhibitor and glinide);
- [14] have been treated with continuous subcutaneous insulin infusion at Visit 1;
- [15] have been treated with drugs that promote weight loss within the 3 months prior to Visit 1;
- [16] are receiving chronic ( $>14$  days) systemic glucocorticoid therapy (excluding topical, intraocular, or intranasal preparations) or have received such therapy within the 4 weeks prior to Visit 1;
- [17] have 1 or more episodes of severe hypoglycemia within the 6 months prior to Visit 1;
- [18] have 1 or more episodes of diabetic ketoacidosis within the 6 months prior to Visit 1;
- [19] have had any of the following cardiovascular conditions within the 3 months prior to Visit 1: acute myocardial infarction (MI), New York Heart Association (NYHA) Class III or Class IV heart failure, or cerebrovascular accident (stroke);

- [20] have a known clinically significant gastric emptying abnormality or have undergone gastric bypass surgery or restrictive bariatric surgery;
- [21] have acute or chronic hepatitis, signs and symptoms of any other liver disease, or alanine aminotransferase (ALT) level >2.5 times the upper limit of the reference range, as determined by the central laboratory at Visit 1;
- [22] have a history of chronic pancreatitis or acute idiopathic pancreatitis, or were diagnosed with any type of acute pancreatitis within the 3 months prior to Visit 1;
- [23] have an estimated glomerular filtration rate (eGFR) <30 mL/min/1.73 m^2, calculated by the Japanese Society of Nephrology equation, as determined by the central laboratory; for participants on metformin, have moderate renal disease or renal dysfunction (for example, eGFR <60 mL/min/1.73 m^2) at Visit 1;
- [24] have any self or family history of type 2A or type 2B multiple endocrine neoplasia (MEN 2A or 2B) in the absence of known C-cell hyperplasia;
- [25] have any self or family history of medullary C-cell hyperplasia, focal hyperplasia, or carcinoma (including sporadic, familial, or part of MEN 2A or 2B syndrome);
- [26] have serum calcitonin  $\geq$ 20 pg/mL, as determined by the central laboratory at Visit 1;
- [27] have evidence of a significant, active uncontrolled endocrine or autoimmune abnormality, as judged by the investigator at Visit 1;
- [28] have a history of transplanted organ;
- [29] have a history of active or untreated malignancy, or are in remission from a clinically significant malignancy during the 5 years prior to Visit 1;
- [30] have a history of any other condition which, in the opinion of the investigator, may preclude the participant from following and completing the protocol;
- [31] have any hematologic condition that may interfere with HbA1c measurement (for example, hemolytic anemias, sickle-cell disease);
- [32] are currently enrolled in any other clinical trial involving an investigational product or any other type of medical research judged not to be scientifically or medically compatible with this study
- [33] have participated, within the last 30 days in a clinical trial involving an investigational product. If the previous investigational product has a long half-life, 3 months or 5 half-lives (whichever is longer) should have passed;
- [34] have previously completed or withdrawn from this study or any other study investigating dulaglutide;

[35] are investigator site personnel directly affiliated with this study and/or their immediate families. Immediate family is defined as a spouse, parent, child, or sibling, whether biological or legally adopted;

[36] are Lilly employees;

[37] are unable and/or unwilling to provide written informed consent, make themselves available for the duration of the study, or abide by study procedures and restrictions.

### **6.3. Lifestyle Restrictions**

Study participants should be instructed not to donate blood or blood products during the study or for 4 weeks following the study.

### **6.4. Screen Failures**

Individuals who do not meet the criteria for participation in this study (screen failure) may not be rescreened.

## 7. Treatments

### 7.1. Treatments Administered

This study involves a comparison of dulaglutide 0.75 mg versus placebo administered once weekly as a subcutaneous injection by single-dose pen (SDP) in patients with T2D who are already treated with insulin with or without 1 or 2 OADs. [Table GBGF.7.1](#) summarizes study treatments and concomitant medications during the primary treatment period, and the extension treatment period.

**Table GBGF.7.1. Study Treatments and Concomitant Medications**

Name of Drug	Dose a	Frequency a	Drug Formulation	Route of Administration
16-Week Primary Treatment Period				
Investigational Compound				
Dulaglutide	0.75 mg	Once weekly	Single-dose pen	Subcutaneous injection
Comparator				
Placebo	Placebo	Once weekly	Single-dose pen	Subcutaneous injection
Concomitant Insulin for Both Treatment Arms				
Basal, mixed, or mealtime insulin	Fixed	Fixed	Pen type device/Vial and syringe	Subcutaneous injection
Oral Antidiabetic Medications for Both Treatment Arms				
Biguanides, TZD, $\alpha$ -GI, SGLT2i	Fixed	Fixed	Tablet	Oral
36-Week Extension Treatment Period				
Dulaglutide	0.75 mg	Once weekly	Single-dose pen	Subcutaneous injection
Basal, mixed, or mealtime insulin	Flexible	Fixed	Pen type device/Vial and syringe	Subcutaneous injection
Biguanides, TZD, $\alpha$ -GI, SGLT2i	Fixed b	Fixed b	Tablet	Oral

Abbreviations:  $\alpha$ -GI = alpha-glucosidase inhibitor; CRP = clinical research physician; CRS = clinical research scientist; OAD = oral antidiabetic; SGLT2i = sodium-glucose co-transporter 2 inhibitor; TZD = thiazolidinedione.

a Dose and frequency refer to investigational compound and concomitant medications within a patient.

b The investigator is to consult with the Lilly CRP or CRS if the dosage of OADs is changed.

The investigator or his/her designee is responsible for the following:

- explaining the correct use of the investigational agent(s) to the patient or patient representative, and SDP training with a demonstration device
- verifying that instructions are followed properly
- maintaining accurate records of investigational product dispensing and collection

#### 7.1.1. Packaging and Labeling

The sponsor will provide dulaglutide and placebo in SDPs, which will be dispensed via an interactive web-response system (IWRS). Each SDP (0.75 mg dulaglutide in 0.5 mL OR

placebo in 0.5 mL) is packaged in cartons of 4 pens. Each carton contains a 4-week supply, as each pen is a weekly dose.

Investigational products will be labeled according to the country's regulatory requirements.

## **7.2. Method of Treatment Assignment**

Patients who meet all criteria for enrollment will be randomized to double-blind treatment at Visit 3. Assignment to treatment groups will be determined by a computer-generated random sequence using an IWRS. The IWRS will be used to assign cartons containing double-blind investigational product to each patient. Site personnel will confirm that they have located the correct cartons by entering a confirmation number found on the carton label into the IWRS.

Randomization will be stratified by insulin regimen (basal insulin, premixed insulin, or basal/mealtime insulin) and HbA1c at Visit 2 ( $<8.5\%$ ,  $\geq 8.5\%$ ) to achieve between-group comparability.

### **7.2.1. Selection and Timing of Doses**

Details of the dosing strategy and administration timing for injectable investigational product, insulin, and concomitant OADs are provided in the following sections.

#### **7.2.1.1. Dulaglutide or Placebo Injections**

All patients will inject investigational product subcutaneously in the abdomen or thigh using the injection supplies provided; a caregiver may administer the injection in the patient's upper arm. A new SDP will be used for each injection.

Investigational product will be administered once weekly. It is recommended that patients inject the investigational product on the same day each week. If the injection is not given on the scheduled day, the missed dose should be given as soon as possible after the scheduled day if there are at least 3 days (72 hours) until the next injection. If fewer than 3 days remain before the next scheduled injection, the missed dose should be skipped and the next dose given at the regularly scheduled time and day.

#### **7.2.1.2. Insulin Treatment**

During the screening period, eligible patients on DPP-4 inhibitor, SU, or glinide will begin a 12-week washout of those medications; these patients may uptitrate their insulin dose for up to 4 weeks, followed by an 8-week stabilization ( $\pm 20\%$  adjustment) of insulin dose prior to Visit 3. For the patients who do not need to wash out, the insulin dose will remain unchanged during the screening and lead-in period.

After completion of the screening and lead-in period, the insulin dose at randomization will be fixed for the 16-week primary treatment period, except for patients who experience repeated or severe hypoglycemia (Section 7.4.1.2). During the 36-week extension treatment period in which all patients will be on dulaglutide and insulin therapy, the investigator will adjust the patient's insulin dose to achieve target blood glucose values (Table GBGF.7.2).

During the whole study period (16-week primary treatment period and 36-week extension treatment period), if repeated hypoglycemia (SMPG  $\leq 70$  mg/dL or symptomatic hypoglycemia) occurs, and it is considered to be related to the pharmacological therapy, the investigator can decrease the dose of insulin any time. If at least 1 episode meets the criteria for severe hypoglycemia (events requiring assistance to administer therapy) or is associated with SMPG  $< 54$  mg/dL recorded during the assessment period, the investigator should decrease the dose of insulin.

